5.4.1.2.1. Decline in HBsAg and HBV DNA Levels

Participants achieving the maximum decline (change from peak level in follow-up to the lowest level achieved during the remainder of follow-up) in the magnitude of the cut-offs as described in Section 5.3.1.1.5 will be evaluated by intervention arm and over time in the follow-up phase only for those participants who restarted NA treatment during the follow-up.

5.4.1.3. Time to Event Endpoints

5.4.1.3.1. HBV RNA <LOD

Time to HBV RNA <LOD is defined as the duration from the date of first study intervention intake to the date of the first occurrence of HBV RNA <LOD (i.e. the date of the first occurrence of HBV RNA <LOD – the date of first study intervention intake + 1). The participant who did not achieve

HBV RNA <LOD or who early withdrew from the study before achieving HBV RNA <LOD will be censored at the last HBV RNA assessment before the date of withdrawal. Only the participants with HBV RNA values \geq LOD+ 0.5 \log_{10} cp/mL (i.e. \geq 2.99 \log_{10} cp/mL) at baseline will be included in this analysis. Similarly, additional analyses only for participants with HBV RNA values \geq LOD+ 1.0 \log_{10} cp/mL and \geq LOD+ 2.0 \log_{10} cp/mL, respectively, will be summarized.

This endpoint will also be analyzed considering participants who were re-treated with NA before achieving the endpoint as censored at the date of NA re-treatment.

5.4.1.3.2. HBcrAg Undetectability

Time to undetectability of HBcrAg is defined as the duration from the date of first study intervention intake to the date of the first occurrence of undetectability of HBcrAg (i.e. the date of the first occurrence of HBcrAg<LLOQ – the date of first study intervention intake + 1). The participant who did not achieve undetectability or who early withdrew from the study before achieving undetectability of HBcrAg will be censored at the last HBcrAg assessment before the date of withdrawal. Only the participants with HBcrAg values \geq LLOQ+ 0.5 \log_{10} U/mL (i.e. \geq 3.5 \log_{10} U/mL) at baseline will be included in this analysis.

This endpoint will also be analyzed considering participants who were re-treated with NA before achieving the endpoint as censored at the date of NA re-treatment.

5.4.1.3.3. Time to Appearance of Anti-HBs Antibodies

Appearance of anti-HBs antibodies is defined as a baseline anti-HBs (quantitative) <LLOQ and a post-baseline assessment \geq LLOQ.

Time to appearance of anti-HBs antibodies is defined as the time (days) from the date of first study intervention intake to the date of the first occurrence of anti-HBs antibodies appearance + 1. The participant who did not experience emergence of antibodies or who early withdrew from the study before showing emergence of anti-HBs antibodies will be censored at the last anti-HBs antibodies assessment before the date of withdrawal.

This endpoint will also be analyzed considering participants who were re-treated with NA before achieving the endpoint as censored at the date of NA re-treatment.

5.4.1.3.4. Time to Appearance of Anti-HBe Antibodies

Appearance of anti-HBe antibodies is defined as a baseline anti-HBe antibodies (qualitative) with a "NEGATIVE" result and a post-baseline assessment with "POSITIVE" result.

Time to appearance of anti-HBe antibodies is defined as the time (days) from the date of first study intervention intake to the date of the first occurrence of anti-HBe antibodies appearance + 1. The participant who did not experience emergence of antibodies or who early withdrew from the study before showing emergence of anti-HBe antibodies will be censored at the last anti-HBe antibodies assessment before the date of withdrawal.

This endpoint will also be analyzed considering participants who were re-treated with NA before achieving the endpoint as censored at the date of NA re-treatment.

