2.4.1. Subgroups for Efficacy Analyses

- Sex: Male, Female
- Age categories: ≤ 45 years, > 45 years
- Type of NA at study entry – stratification levels:
 - TDF/TAF
 - Entecavir (ETV)
- Type of NA at study entry – categorization levels
 - TDF
 - TAF
 - ETV
- Duration of NA (see Section 4.2.2): > 2 years to ≤ 4 years, > 4 years to ≤ 8 years, > 8 years
- Race: Asian, non-Asian

- HBsAg level at baseline – stratification levels:
 - <1,000 IU/mL
 - \geq 1,000 IU/mL
- HBsAg level at baseline – categorization levels:
 - <1,000 IU/mL
 - \geq 1,000 IU/mL-<10,000 IU/mL
 - \geq 10,000 IU/mL
- HBV DNA level at baseline:
 - <LLOQ TND
 - < LLOQ TD
 - <LLOQ
 - \geq LLOQ
- HBV RNA level at baseline:
 - Negative
 - < 1,000 copies /mL
 - \geq 1,000 copies /mL
- HBcrAg level at baseline:
 - <3 log U/mL
 - \geq 3 log U/mL-<4 log U/mL
 - \geq 4 log U/mL
- HBsAg Antibody (Anti-HBs) level at baseline:
 - <LLOQ
 - \geq LLOQ
 - <10 mIU/mL
 - \geq 10 mIU/mL
- Alanine Transferase (ALT) at baseline: \leq 1.0 ULN, > 1.0 ULN - <2.5 ULN, \geq 2.5 ULN
- Anti-HBe antibody at baseline: Positive, Negative

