5. EFFICACY

All efficacy data will be analyzed by intervention arm, analysis phase and over time (when applicable). The primary analysis set will be the mITT analysis set (see definition in Section 2.3). Selected efficacy endpoints will be also analyzed using the ITT and PP analysis sets, respectively (see definition in Section 2.3). Efficacy assessments over time will be performed at the analysis time points defined in Section 2.1.

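### SAP 5.4.1.3.3 and 5.4.1.3.4 set no entry rule for time to antibody appearance, so read literally, baseline-positive participants who cannot have the event stay in the risk set and dilute the cumulative incidence

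*SAP*

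**What the plan says.** Both event definitions contain a baseline condition. For anti-HBe, SAP 5.4.1.3.4 states: "Appearance of anti-HBe antibodies is defined as a baseline anti-HBe antibodies (qualitative) with a" negative result, followed by a positive one. For anti-HBs, SAP 5.4.1.3.3 states: "Appearance of anti-HBs antibodies is defined as a baseline anti-HBs (quantitative) <LLOQ and a post-baseline assessment" at or above the LLOQ.

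Both sections then censor at the last antibody assessment. The anti-HBe rule applies to "The participant who did not experience emergence of antibodies or who early withdrew from the study before showing emergence of anti-HBe antibodies"; the anti-HBs rule applies to "The participant who did not experience emergence of antibodies or who early withdrew from the study before showing emergence of anti-HBs antibodies". Neither adds an entry condition.

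The two preceding endpoints do. SAP 5.4.1.3.1 has a sentence beginning "Only the participants with HBV RNA values" and SAP 5.4.1.3.2 one beginning "Only the participants with HBcrAg values"; each sets a baseline threshold for inclusion.

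Nothing elsewhere supplies the missing limit. SAP 5.4.2.3 refers to SAP 5.3.2.3 (Kaplan-Meier cumulative incidence, median, log-rank test, stratified Cox model), which sets none. SAP 5 gives the default: "The primary analysis set will be the mITT analysis set". That set is not defined by antibody status.

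Baseline positives are foreseen. SAP 2.4.1 lists "Anti-HBe antibody at baseline: Positive, Negative" as a subgroup and splits baseline anti-HBs at the LLOQ. SAP 5.4.2.2.3 plans a summary for participants with positive anti-HBs at baseline.

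**The concern.** A participant who is antibody-positive at baseline cannot meet either definition at any visit. Under the censoring rule as worded, that participant is nevertheless followed as a non-event and counted in every risk set up to the last assessment. The curve then answers how much new antibody appears in the whole analysed group, including people for whom the question does not arise. Most readers would take a time-to-appearance curve to describe people who start without the antibody.

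At stake are the height of the two curves, the planned median and quartiles, and some sensitivity of the log-rank test. Two programmers could also produce different curves from the same text.

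**Working it through.** **Inputs.** Event definitions and censoring rules: SAP 5.4.1.3.3 and 5.4.1.3.4. Estimator and test: SAP 5.3.2.3. Arm sizes 80 and 40: SAP 1.4. One-sided 0.05: SAP 5.1.1. The baseline-positive share q and all conversion rates are assumptions, because the documents give neither. The plan states no figure for these endpoints, so there is none to reproduce.

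**Dilution.** Let F(t) be the cumulative incidence among baseline-negative participants. If a share q can never have the event and is censored like everyone else, the survival function of the mixed group is q + (1-q)(1-F(t)), so the curve estimates

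1 - [q + (1-q)(1-F(t))] = (1-q) F(t).

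With F = 30%: q = 30% gives 0.7 x 30 = 21%; q = 60% gives 0.4 x 30 = 12%; q = 90% gives 0.1 x 30 = 3%.

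**Median.** It is reached only if (1-q)F is at least 50%, that is F at least 0.5/(1-q). At q = 30% this needs F of 0.5/0.7 = 71%; at q = 50% it needs 100%. At about q = 50% or more the median will generally not be reached, whatever the drug does.

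**Simulation check.** Arms of 80 and 40, 10% dropout, 1,500 runs, assumed visits at Weeks 24, 44, 48, 52, 60, 72, 84 and 96, and assumed Week 96 incidence among baseline-negatives of 50% (Arm 1) and 25% (Arm 2). Restricted to baseline-negatives, Kaplan-Meier returned about 50% and 25% at every q. Without the restriction:

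| q | Kaplan-Meier, Arm 1 / Arm 2 | (1-q)F | Log-rank power, unrestricted | Log-rank power, restricted |
|---|---|---|---|---|
| 10% | 45.1% / 22.1% | 45.0% / 22.5% | 80% | 83% |
| 30% | 35.1% / 17.2% | 35.0% / 17.5% | 66% | 71% |
| 50% | 25.1% / 12.5% | 25.0% / 12.5% | 48% | 56% |
| 70% | 14.9% / 7.7% | 15.0% / 7.5% | 28% | 38% |
| 90% | 5.1% / 2.7% | 5.0% / 2.5% | 5% | 15% |

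The formula holds within half a point. With equal q in both arms the ratio of incidences is preserved, but the difference shrinks: 25 points becomes 0.3 x 25 = 7.5 at q = 70%.

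**Chance imbalance in q.** Baseline antibody status is not a stratification factor (SAP 1.5). At q = 70% the SD of the between-arm difference in q is sqrt(0.7 x 0.3 x (1/80 + 1/40)) = 8.9 points. Suppose F is 30% in both arms and q happens to be 60% and 70%. The curves read 0.4 x 30 = 12% and 0.3 x 30 = 9%. That 3-point gap has a standard error of sqrt(0.12 x 0.88/80 + 0.09 x 0.91/40) = 5.8 points, so it is about half a standard error. It is noise, and the restriction removes it.

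**The case against.** **The SAP never says that baseline positives are kept.** True. A negative baseline is part of the definition, and a careful programmer might infer the restriction. The defect is an omission. But the text does not require that inference, and the default set includes these participants.

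**The neighbouring endpoints are not a clean contrast.** Also fair. For HBV RNA and HBcrAg the event has no baseline condition, so without an entry rule people already below the limit would count as immediate events. Those rules also demand a margin of at least 0.5 log10 above the limit. A reader might infer from the contrast that the authors meant to keep antibody-positive participants; the documents do not show that. The contrast shows only that an entry rule is stated for two endpoints and missing for the other two.

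**The unrestricted curve is a valid quantity.** It estimates new appearance in the whole analysed population, and HBsAg seroconversion (SAP 5.3.1.1.4) uses the same anti-HBs baseline condition without limiting the population. This stands, so calling the estimate simply wrong would go too far. It is a less useful quantity, because its height depends on the baseline mix and its quantiles may not exist.

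**Arm bias.** A reader might infer that imbalance in baseline status creates a false treatment effect. It does not: under randomisation such imbalance is ordinary sampling error, favours neither arm systematically and does not inflate the log-rank type I error.

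**Size.** A reader might also infer that most participants are anti-HBe-positive because all must be HBeAg-negative. The documents give no share, and that argument says nothing about anti-HBs. If q is small, the effect is small.

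**Conclusion.** The point holds as a dilution problem in two exploratory analyses. Followed literally, SAP 5.4.1.3.3 and 5.4.1.3.4 keep participants who cannot have the event in the risk set, and the reported cumulative incidence is about (1-q) of the incidence among those at risk. This rests on similar censoring in baseline-positive and baseline-negative participants and on a q that the documents leave open and that may differ between the two antibodies. Under the assumed 50% and 25% incidences, the power lost is 3 points at q = 10% and 10 points at q = 70%.

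No primary or secondary conclusion depends on these curves. For anti-HBe, the shift tables in SAP 5.4.2.1 show part of the same data by baseline status, though without a time-to-event estimate; that section plans no such table for anti-HBs. The correction is still worth making, because the direction of the error is predictable and the remedy is specific.

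**What to change.** Add to SAP 5.4.1.3.3: *Only participants with baseline anti-HBs <LLOQ enter this analysis.* Add to SAP 5.4.1.3.4: *Only participants with a NEGATIVE baseline anti-HBe enter this analysis.* Say how a missing baseline result is handled, and report the number at risk by arm with each curve. Note beside the anti-HBs result that its denominator now differs from that of HBsAg seroconversion in SAP 5.3.1.1.4.

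The cost is a sentence or two per section and a smaller analysis set. No information on the event is lost, since the excluded participants cannot contribute one, and no extra data are needed.

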5.4.2. Analysis Methods

Statistical comparisons of all exploratory endpoints between intervention arms will be done with no adjustment for multiplicity.

5.4.2.1. Binary Endpoints

The number and proportion (%) of participants achieving the endpoints defined in Section 5.4.1.1 will be summarized. The associated 90% CI may also be included.

Participants who achieve partial cure at 24 weeks and 48 weeks after stopping all study interventions will be compared between treatment interventions using the Mantel-Haenszel test and 90% CIs adjusted for the stratification factors. Similar analysis for the impact of finite treatment duration on functional cure will also be done.

Shift tables in Anti-HBe positive/negative values from baseline will also be provided at each time point.

5.4.2.2. Continuous Endpoints

The values of and changes from baseline in anti-HBs antibodies will be summarized only descriptively in a similar manner as described for values and changes from baseline over time in other blood disease markers in Section 5.3.2.2.

Waterfall plots for changes from baseline of HBV RNA, HBcrAg and fibrosis will also be presented.

Subsections below describe the additional analyses planned for only those specific exploratory endpoints that require further evaluations.

5.4.2.2.1. Fibrosis

The changes from baseline at end of study intervention and follow-up will be summarized using descriptive statistics (for example, may include n, mean, SD, 90% CI, median, minimum, maximum) by intervention arm. The comparison between intervention arms will be done using ANCOVA with intervention arm, randomization stratification factors as main effects in the model and baseline score as covariate.

At each assessment time point, a frequency distribution of severity scores will be produced by intervention arm. A graphical display will also illustrate the findings.

5.4.2.2.2. HBV RNA and HBcrAg

The changes from baseline value to nadirs (i.e. maximum decrease for each participant) in HBV RNA and HBcrAg, respectively, and the various graphical displays will be presented.

5.4.2.2.3. Anti-HBs

For participants with positive anti-HBs antibodies at baseline who will reach HBsAg seroclearance (as defined in Section 5.2.1), descriptive statistics will be calculated for the change of anti-HBs antibodies level from baseline at the timepoint when achieving the HBsAg seroclearance by intervention arm. In an additional summary, the change of anti-HBs antibodies level from baseline at the specific timepoint (i.e. Week 48, Week 72, Week 96) will be summarized descriptively for the subset of the participants achieving HBsAg seroclearance at any time before or at that given timepoint by intervention arm.

Cross-tabulations overtime of quantitative versus qualitative anti-HBs values, respectively, will also be presented.

5.4.2.3. Time to Event Endpoints

The time-to-event analyses will be analyzed in a similar manner as for the time to event endpoints described in the Section 5.3.2.3.

6. SAFETY

All safety analyses will be performed using the safety analysis set. All assessments will be presented by analysis phase, unless other specified. All summaries will be descriptive, and no inferential methods will be used to compare intervention arms for safety.

Safety and tolerability will be assessed by evaluating treatment emergent-adverse events (TEAEs), physical examinations, vital signs measurements, clinical laboratory tests (including hematology, blood biochemistry, blood coagulation, and urinalysis), and ECGs.

Continuous parameters will be summarized using the following statistics: number of observations, mean, standard deviation (SD), standard error (SE), minimum, median and maximum, unless specified otherwise. Frequencies and percentages will be used for summarizing categorical (discrete) data.

As a result of the IDMC ongoing reviews to ensure the continuing safety of study participants, additional safety analyses may be generated at the discretion of the Sponsor.

6.1. Adverse Events

6.1.1. Definitions

The verbatim terms used in the CRF by investigators to identify adverse events will be coded using the Medical Dictionary for Regulatory Activities (MedDRA version 21.1 or higher). Treatment-emergent AEs (TEAE) are all AEs with a start date on or after the first administration of study treatment or any ongoing event that worsens in severity, intensity or frequency after the first administration of study treatment. If the event date and/or resolution date is recorded as partial or completely missing, then the imputation rules described in Section 2.5.1 will apply.

6.1.2. Analysis Methods

The adverse events will be summarized by intervention arm and by analysis phase. Adverse events will be allocated to phases based on their start date. If the start date of an event falls between (or on) the start and stop date of a study phase, the AE will be attributed to that phase (treatment-emergent principle). For imputation of partially/fully missing dates please see Section 2.5.1. In case of a completely missing start date, the event is allocated to the double-blind study intervention phase, except if the end date of the AE falls before the first administration of study treatment (DB Day 1).

An overview table will summarize the incidence of TEAEs classified in the following categories: AEs, serious AEs, related AEs, AEs leading to treatment discontinuation, and fatal AEs by presenting by intervention arm the number and percentage of participants who experienced at least one of such AE. The overview AEs table will be also presented stratified by the subgroup of interests identified in Section 2.4.2.

AE relationship to study treatment is grouped into either related or not related category. A related AE is defined as with possible, probable, or very likely relationship with study treatment; not related, otherwise.

All adverse events will be presented in a descending order by incidence based on all participants (Total column). The following TEAEs tables will be included in the analysis:

- All TEAEs
- Serious TEAEs
- At least grade 3 TEAEs
- At least grade 2 TEAEs and related
- TEAEs leading to treatment discontinuation
- Related TEAEs

All serious TEAE, related TEAE, TEAE leading to death, TEAE leading to discontinuation, TEAE of at least grade 3, or adverse events of special interest (AESIs) will be listed separately. Listings will include all information collected on the Adverse Event CRF pages (e.g. information on time of onset, duration of events, time of resolution, concomitant therapies and relationship to study treatment).

For participants reporting rash, a listing with specific grade will be provided and Rash questionnaire will be tabulated by study intervention arm and overall.

6.1.3. Adverse Events of Special Interest

Incidence of treatment-emergent adverse events of special interest will be summarized by intervention arm and analysis phase. The adverse events of special interest include:

- ALT/AST elevations

- Injection Site Reactions
- Renal complications
- Cholesterol increase
- Hematologic abnormalities (platelet count, hemoglobin, reticulocytes, neutrophil count)

The list of all preferred terms belonging to ALT/AST elevations, renal complications, cholesterol increase, and hematologic abnormalities is provided in [Attachment 2](#). Injection site reactions will be identified using the eCRF Injection Site Reaction form.

6.2. Clinical Laboratory Tests

6.2.1. Definitions

Laboratory data from the central laboratory will be summarized by category of laboratory test. The different categories and laboratory tests used in the analysis are listed in [Table 4](#). The tests will be allocated to the categories in the table.

Table 4: Laboratory Parameters to Be Summarized

Laboratory Category	Parameters		
Hematology	Platelet count RBC count Hemoglobin Hematocrit Reticulocyte count Reticulocyte index	RBC Indices: Mean corpuscular volume Mean corpuscular hemoglobin Mean corpuscular hemoglobin concentration % Reticulocytes	WBC count with Differential: Neutrophils Lymphocytes Monocytes Eosinophils Basophils
Hematology Coagulation	Activated partial thromboplastin time Prothrombin Intl. normalized ratio Prothrombin time		
Clinical Chemistry	Sodium Potassium Chloride Bicarbonate Blood urea nitrogen Creatinine Glucose AST/Serum glutamic-oxaloacetic ALT/Serum glutamic-oxaloacetic Gamma-glutamyltransferase (GGT) Total, conjugated and unconjugated bilirubin Alkaline phosphatase Creatine phosphokinase	Lactic acid dehydrogenase Uric acid Calcium Phosphate Albumin Total protein Total cholesterol High-density lipoprotein cholesterol Low-density lipoprotein cholesterol Triglycerides Magnesium Lipase Amylase	
Note: Creatinine clearance (eGFR calculated by the CKD-EPI formula) will be assessed.			

Routine Urinalysis	Dipstick Specific gravity pH Glucose Protein Blood Ketones Bilirubin Urobilinogen Nitrite Leukocyte esterase	Sediment (if dipstick result is abnormal) RBCs WBCs Epithelial cells Crystals Casts Bacteria
Urine Chemistry (quantitative measurement)	Creatinine Sodium Phosphate	Glucose Protein Albumin
Renal Biomarkers	Retinol binding protein Beta-2-microglobulin	

The laboratory abnormalities will be determined according to the criteria specified in the DAIDS Toxicity Grading Scale (see Clinical Protocol Section 10.9, Appendix 9, DAIDS Table) or in accordance with the normal ranges of the clinical laboratory if no gradings are available.

An assessment is treatment-emergent if the toxicity grade/abnormality worsened as compared to the grade/abnormality at baseline; this also includes the shift from abnormally high to abnormally low and vice-versa. Post-reference toxicities/abnormalities are always treatment-emergent with regard to missing toxicities/abnormalities at baseline. The abnormalities 'Abnormally high' and 'Abnormally low' are considered equally important.

For each lab parameter, a worst-case analysis will be performed by using the worst abnormality and/or worst toxicity grade lab value and time point per participant. The worst toxicity case is the value associated to the highest toxicity grade and is derived per parameter and toxicity direction (hypo / hyper). Worst-case will be derived within each phase, including unscheduled assessments. For abnormalities, in case the same subject has both abnormalities (low and high) for the same lab test within the same phase, the participant will be counted in the analysis for both toxicity directions (abnormally high and low).

Change from baseline will be evaluated for all time points when assessed and is defined as follows: value at a given time point minus baseline value.

Imputation rules:

In case continuous laboratory results are not numerically expressed, but as a character (e.g. 'less than 2', '>25'), these results will be numerically imputed as follows:

- If the analysis result contains '<' then the result will be multiplied by 0.999 (e.g. <6.1 becomes 6.0939).
- If analysis result contains '>' then the result will be multiplied by 1.001 (e.g. >6.1 becomes 6.1061).

- If analysis result contains ' \leq ' or ' \geq ' then only the numeric portion of the result will be used. This also applies to normal limits expressed as such.

